10.1.1 Subject Re-Screening

This study permits the re-screening of a subject who has discontinued the study as a pre-treatment failure (i.e., subject has not been dosed with IMP); the reason for failure must be temporary and expected to resolve. If re-screened, the subject must be re-consented.

10.2 Admission and Pre-dose Procedures

The identity of the subjects will be confirmed at each admission and pre-dose.

In addition, the ongoing eligibility of subjects will be re-assessed at admission/pre-dose, as described in [Sections 9.2 and 9.3](#).

Admission/pre-dose safety procedures such as clinical laboratory tests, ECGs, vital signs, urinalysis and drugs of abuse tests can be repeated as clinically indicated under the discretion of Investigator or Sub-investigator if there is a concern regarding a subject's safety or eligibility to participate in the clinical trial.

Reserve subjects for the first dose occasion, in any group, will not require admission procedures to be repeated, if dosing is within 2 days.

If dosing is delayed, subjects who have completed admission procedures do not need admission procedures to be repeated if dosing is within 2 days and the subjects have remained resident in the clinical unit.

The subjects will be admitted to the clinical unit in the morning on the day before dosing (Day -1) in Period 1, and in the evening on the day before dosing (Day -1) in Period 3 and optional Period 4. Subjects will remain resident in the clinical unit between Periods 1 and 2; therefore, no admission procedures will be conducted for Period 2.

In addition, subjects may be required to visit the clinical unit on Day -1 of Periods 1, 3, and optional Period 4, prior to admission to the clinical unit, for SARS-CoV-2 antigen tests (if required; see [Sections 6.4.2.2](#) and [14.5.8](#)).

The admission and pre-dose procedures are presented in the schedule of assessments.

10.3 Study Day Procedures

10.3.1 Blood Volume

[figure not shown]
The number and timing of samples may be amended following any interim PK parameter estimations. However, in this case, the total blood volume for each subject will not exceed 550 mL in a 4-week period.

The first 0.5 mL of blood withdrawn via cannula will be discarded.

10.3.2 Timing of Procedures

There are times where the protocol requires more than one procedure to be completed at the same time point.

As guidance, the preferred order of assessments is:

All safety assessments will be timed and performed relative to the start of dosing.

10.3.3 Discharge from the Clinical Unit

A subject will be allowed to leave the premises without additional Investigator or Sub-investigator review, following completion of study-specific procedures providing that:

- No AEs have been reported during the study visit
- The subject responds in the affirmative when asked if they are feeling well

Refer to [Section 8.1](#) for further details, and the schedule of assessments for study-specific procedures at subject discharge. As subjects will remain resident in the clinical unit between Periods 1 and 2, discharge procedures will apply to Periods 2 to 4 only.

If any of these conditions are not met, then the subject will only be allowed to leave the clinical unit with the authorisation of the Investigator or Sub-investigator.

There will be no continued provision of the study intervention or treatment for subjects, as this study involves healthy volunteers only.

10.3.4 Medical Supervision

A physician will be responsible for the clinical aspects of the study and will be available at all times during the study. In accordance with the current Association of the British Pharmaceutical Industry guidelines [10], each subject will receive a card stating the telephone number of the Investigator and the 24/7 contact details of the Quotient Sciences' on-call physician.

10.3.5 Follow-up

A follow-up phone call will take place on Day 6 ± 1 of the final treatment period, to ensure the ongoing wellbeing of the subjects. If a subject reports any AEs that present a cause for concern, they will be required to attend the clinical unit for an (unscheduled) follow-up visit; assessments may be performed at the unscheduled follow-up visit, as detailed in the schedule of assessments. Completion of the last follow-up phone call or unscheduled follow-up visit will be considered the end of the study.

11 Dosing of Subjects

Dosing will be performed at the time points detailed in the study schedule of assessments in [Appendix 2](#).

11.1 Food and Fluid Intake

Subjects will be allowed water up to 1 hour before the scheduled dosing time and will be provided with 240 mL of water at 1 hour post-dose (to ensure adequate hydration) and thereafter, water will be allowed ad libitum after 1 hour post-dose. Decaffeinated fluids will be allowed ad libitum from lunch time on the day of dosing.

If, for technical reasons, dosing is delayed for more than 2 hours beyond the expected dosing time, subjects will receive 200 mL of an electrolyte drink (e.g., Lucozade Sport) at the originally scheduled dosing time, or earlier if possible.

Fasted Dosing

Fasted dosing will apply to regimens in Periods 1 and 2, and may apply to regimens in Period 3 or optional Period 4, unless fed dosing is selected during the relevant interim decision meeting, based on available PK and safety data.

The calorie/fat content of meals are not required to be controlled. Subjects will be provided with a standardised menu.

Subjects will be provided with a snack and then fast from all food and drink (except water) for a minimum of 10 hours on the day prior to dosing until approximately 4 hours post-dose, at which time lunch will be provided. An evening meal will be provided at approximately 10 hours post-dose and an evening snack at approximately 14 hours post-dose. On subsequent days, meals will be provided at appropriate times.

Fed Dosing

Fed dosing may be selected for regimens in Period 3 or optional Period 4.

The calorie/fat content of breakfast will be controlled on Day 1 (refer to [Appendix 4](#) for breakfast content). Subjects will be provided with a standardised menu for all other meals.

For fed regimens, a high-fat breakfast will be given approximately 30 minutes before dosing.

Subjects will be provided with a snack and will fast for a minimum of 10 hours from all food and drink (except water) until the following morning, when they will be provided with a high-fat breakfast.

The breakfast should be consumed over a maximum period of 25 minutes, with dosing occurring 30 ± 5 minutes after the start of breakfast. Subjects should be encouraged to eat their meal evenly over the 25 minute period. It is acknowledged that some subjects will take less time to eat, but dosing should still occur 30 ± 5 minutes after the start of breakfast. Subjects must consume at least 90% of the pre-dose breakfast in order to be eligible for dosing. The start and stop time and percentage of the breakfast consumed must be recorded in the source.

Lunch will be provided at approximately 4 hours post-dose, an evening meal at approximately 10 hours post-dose and an evening snack at approximately 14 hours post-dose. On subsequent days, meals will be provided at appropriate times.

11.2 Administration of Test Preparations

Specific details of IMPs, and doses to be administered, are provided in [Section 5.2](#) and [Section 8.1](#), respectively. Subjects will be dosed on the morning of Day 1 of each study period.

The exact time of dosing will be decided based on logistics and will be documented in the source. The order in which regimens are dosed may be subject to change due to logistical reasons.

The minimum washout period between regimens may be changed, if data collected during the study support the change. However, the minimum washout period will not be reduced to less than 5 half-lives of the IMP.

Subjects will receive single administrations of delafloxacin on up to 4 separate occasions.

Oral tablets will be administered with a total of 240 mL of water. If required, additional water may be given with the IMP in 50 mL aliquots and will be recorded in the source but will not be classed as a protocol deviation.

Immediately after administration of delafloxacin Powder for Oral Suspension, the dosing vessel will be rinsed with water and subjects will consume the rinse solution. Subjects will then consume further water to a total volume of 240 mL (including the dosing volume and volume used to rinse the dosing vessel). If required, additional water may be given with the IMP in 50 mL aliquots and will be recorded in the source but will not be classed as a protocol deviation.

11.3 Dosing Compliance

During all clinical phases of the study, subjects will be observed by study staff to assure compliance to all study procedures, including dose administration.

Mouth and hand checks will be conducted after dosing, as applicable, to ensure that the IMP has been swallowed.

The date and time that each subject is dosed will be recorded in the subject's source data. Any violation of compliance will require evaluation by the Investigator and Sponsor to determine if the subject can continue in the study.

11.4 Prior and Concomitant Medications

No prescribed, over-the-counter medication or herbal remedies will be permitted from 14 days before the first dose of IMP until the follow-up phone call, except up to 4 g of paracetamol per day, hormonal contraception, or HRT, and those deemed necessary by the Investigator to treat AEs (see also [Section 9.3](#)). Any medications used will be recorded in the source.

Subjects are not permitted to receive antibacterial medications, antacids, medications containing multivalent cations or metal cations, multivitamin preparations containing zinc or iron, or didanosine buffered tablets in the 14 days before the first dose of IMP until the follow-up phone call.

Subjects are not permitted to receive a COVID-19 vaccine within 2 days (48 hours) prior to each admission, so that by the time of dosing, any effects of the vaccine (e.g., pyrexia, fatigue, pain/stiffness at site of injection) are likely to have abated. Additionally, COVID-19 vaccines will not be accepted concomitant medications for the duration of the study.

Emergency equipment and drugs will be available within the clinical unit as per current standard procedures. In the unlikely event that they are required, their use will be documented.

Medication taken within 14 days of informed consent will be recorded in the source.

12 Assessment of Efficacy

Not applicable for this Phase 1 study.

13 Assessment of Pharmacokinetics, Taste/Palatability and Pharmacodynamics

PK assessments will be performed as detailed in the study schedule of assessments in [Appendix 2](#).

13.1 Assessment of Pharmacokinetics

13.1.1 Pharmacokinetic Blood Sampling

Venous blood samples will be collected from the subjects by a trained member of the clinical team. Consent will be collected from the subjects for use of these samples for the purposes of the proposed study. Samples will be processed to isolate plasma and PK analysis will be carried out on plasma samples.

Plasma samples will be sent for laboratory testing in linked anonymised form (subject number only). This information is able to be linked directly to the volunteer by the Quotient Sciences research team and study monitor, however not by the laboratory staff or Sponsor.

Venous blood samples will be withdrawn via an indwelling cannula or by venepuncture at the time points detailed in the schedule of assessments.

All PK windows will be timed relative to the start of dosing for each period.

The acceptable deviations from the nominal blood sampling times are as follows:

- Day 1: The pre-dose sample will be taken \leq 1 hour before dosing.
- 0 to 1 hour post-dose samples will be taken within \pm 2 minutes of the nominal post-dose sampling time.
- 1.5 hours to 12 hours post-dose samples will be taken within \pm 10 minutes of the nominal post-dose sampling time.
- 14 hours to 48 hours post-dose samples will be taken within \pm 30 minutes of the nominal post-dose sampling time.

The timing and number of the samples may be amended following any interim PK parameter estimations, including collection over a longer duration. Any changes to blood sampling time points would be documented in the interim dose decision report and retained in the ISF.

Samples will be collected into appropriate tubes as specified by the bioanalytical laboratory. Details of sample tubes and processing will be contained in the Clinical Sample Processing Manual (CSPM).

Samples will be shipped to PPD, Inc. for the analysis of delafloxacin.

13.2 Assessment of Pharmacodynamics

Not applicable for this Phase 1 study.

13.3 Taste/Palatability Evaluation

Taste/palatability will be assessed using a questionnaire (example provided in [Appendix 3](#)) at the time points detailed in the schedule of assessments. The questionnaire will ask subjects to rate the overall acceptability of taste/palatability of each of the delafloxacin Powder for Oral Suspension (i.e., test) regimens, with additional questions asked on specific taste/palatability attributes (smell, sweetness, bitterness, flavour, mouth feel/texture, grittiness, and aftertaste), on a 9-point scale [\[11\]](#). The clinical staff will provide definitions and examples of each aspect that is being rated if required. Subjects will be asked to rate each test regimen independently of any previous taste/palatability questionnaires.

Each subject will complete the questionnaire individually and privately following each test IMP administration.

The questionnaire will be started within 10 minutes of test IMP administration.

14 Assessment of Safety

Safety assessments will be performed as detailed in the study schedule of assessments in [Appendix 2](#).

14.1 Definition and Classification of Adverse Events

An AE is any untoward medical occurrence in a subject that occurs either before dosing (referred to as a pre-dose AE) or once a medicinal product has been administered, including occurrences which are not necessarily caused by or related to that product.

An ADR is any AE where a causal relationship with the IMP is at least a reasonable possibility (possibly related or related).

AEs will be monitored from the time that the subject signs the ICF until after the follow-up phone call/unscheduled follow-up visit. The severity of AEs should be assessed as follows:

- Mild** An AE that is easily tolerated by the subject, causes minimal discomfort and does not interfere with everyday activities.
- Moderate** An AE that is sufficiently discomforting to interfere with normal everyday activities; intervention may be needed.
- Severe** An AE that prevents normal everyday activities; treatment or other intervention usually needed.

14.2 Assessment of Causality

Every effort should be made by the Investigator to try to explain each AE and assess its relationship, if any, to the IMP. The temporal relationship of the event to IMP administration should be considered in the causality assessment (i.e., if the event starts soon after IMP administration and resolves when the IMP is stopped).

Causality should be assessed using the following categories:

- Unrelated:** Clinical event with an incompatible time relationship to IMP administration, and that could be explained by underlying disease or other drugs or chemicals or is incontrovertibly not related to the IMP.
- Possibly related:** Clinical event with a reasonable time relationship to IMP administration, and that is unlikely to be attributed to concurrent disease or other drugs or chemicals.
- Related:** Clinical event with plausible time relationship to IMP administration and that cannot be explained by concurrent disease or other drugs or chemicals.

The degree of certainty with which an AE is attributed to IMP administration (or alternative causes, e.g., natural history of the underlying disease, concomitant therapy) will be determined by how well the experience can be understood in terms of one or more of the following:

- Known pharmacology of the IMP.
- Reactions of a similar nature have been previously observed with the IMP or this class of drug.
- The experience being related by time to IMP administration, terminating with IMP withdrawal or recurring on re-challenge.
- Alternative cause.

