8.5 Stopping Criteria

The study will be halted, and the risk to other subjects evaluated if any of the following criteria are met:

- A SAR (i.e., a SAE considered at least possibly related to the IMP administration) in 1 subject.
- Severe non-serious adverse reactions (i.e., severe non-serious AE considered as at least possibly related to the IMP administration) in 2 subjects in the same cohort, independent of within or not within the same system organ class.

Relatedness to IMP will be determined by the Investigator.

If the study is halted, a temporary halt will be submitted to the Medicines and Healthcare products Regulatory Agency (MHRA) and ethics committee (EC) in the form of a substantial amendment. The study may be resumed or terminated; however, it will not be resumed until a further substantial amendment to resume the study is submitted and approved by MHRA and EC.

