11.3 Adverse Events

Throughout the study, all adverse events (AE) will be evaluated by the PI and noted in the AE section of the eCRF study build specification. An AE is any untoward medical occurrence in a subject that occurs either before dosing (referred to as a pre-dose AE) or once a medicinal product has been administered, including occurrences which are not necessarily caused by or related to that product.

AEs will be coded using the Medical Dictionary for Regulatory Activities (MedDRA v27.0), and reported by system organ class (SOC) and preferred term (PT) PT.

AEs will be classified into the following categories:

- Pre-dose AEs: AEs recorded at screening or with a start date and time prior to the first dose of IMP
- Treatment-emergent adverse events (TEAEs): AEs that commence during/after the first dose of IMP or commence before first dose of IMP (i.e. a pre-dose AE or existing medical condition) but worsen in intensity during exposure to IMP

TEAEs will be assigned to the regimen of the period in which the AE first occurred. Where the severity of an AE intensifies or symptoms change in a subsequent period, this will be defined as a new AE and included under the regimen associated with the subsequent period. AEs that occur during the washout period will be assigned to the regimen the subject received during the period immediately before the washout period.

Adverse events will be classified as “mild,” “moderate,” or “severe” when considering their severity.

Adverse events will be classified as “unrelated”, “possibly related,” and “related” when considering their relationship to IMP. TEAEs classified as “possibly related” and “related” will be defined as IMP-related events. An adverse drug reaction (ADR) is any AE where a causal relationship with the IMP is at least reasonable possibility, i.e., “possibly related” and “related”. Pre-dose AEs will always have the classification of “unrelated”.

If the severity or relationship to IMP of a TEAE is missing, the severity/relationship will be tabulated as “missing” in the summary tables.

When summary presentation is made by maximum severity, “missing” will be handled as follows:

- If there are other events (i.e., same SOC and PT code) with a maximum severity recorded as “moderate” or “severe” for that subject and regimen, then the maximum observed severity for that subject will be categorised and presented as “moderate” or “severe”, respectively

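### Protocol 14.2 has no causality category for an event with compatible timing and a plausible disease or drug cause, although 14.1 and SAP 11.3 can make that event an ADR

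*Protocol*

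**What the plan says.** Protocol 14.2 directs that causality be assessed with three categories:

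- *Unrelated* has two limbs. The first is "Clinical event with an incompatible time relationship to IMP administration, and that could be explained by underlying disease or other drugs or chemicals"; the second adds "or is incontrovertibly not related to the IMP".
- The middle label, *possibly related*, is for one "with a reasonable time relationship to IMP administration, and that is unlikely to be attributed to concurrent disease or other drugs or chemicals".
- The bar for *related* is higher still: plausible timing, and no concurrent illness, other medicine or chemical able to account for the event.

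The section closes with four considerations bearing on the degree of certainty: known pharmacology, earlier similar reactions, time relation and alternative cause. It does not say which label mixed evidence should receive.

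Protocol 14.1 defines an ADR as any AE "where a causal relationship with the IMP is at least a reasonable possibility", and equates this in brackets with the labels *possibly related* and *related*. SAP 11.3 repeats it: "An adverse drug reaction (ADR) is any AE where a causal relationship with the IMP is at least reasonable possibility". The SAP uses the same three labels, defines none of them further, and calls TEAEs with either positive label IMP-related.

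The label has consequences. Under Protocol 8.5 the study halts for one SAE judged at least possibly related, or for severe non-serious AEs judged at least possibly related in two subjects of the same cohort. On who judges, 8.5 says: "Relatedness to IMP will be determined by the Investigator". Protocol 8.4 bars replacement of a subject withdrawn for an IMP-related AE. SAP 11.3.1.4 and 11.3.1.5 tabulate events by relationship and tabulate ADRs.

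**The concern.** A competing explanation does not remove a reasonable possibility that the drug caused an event. Protocol 14.1 and SAP 11.3 accept this. The definition of *possibly related* in 14.2 does not, because it requires the competing explanation to be unlikely. Two rules in the plan therefore give different answers for the same event, and the one that the Investigator is told to use for labelling is the narrower.

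The label decides whether the event counts towards a halt. With a one-subject and a two-subject trigger, a single label can be decisive. For an event in the gap, any label that the Investigator chooses departs from the text of 14.2, and two careful assessors could reach opposite results.

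**Working it through.** There is no planned figure to reproduce. The check is whether the three definitions cover every event.

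**Inputs, all from Protocol 14.2.** Each event is described by its timing (compatible or incompatible), by the status of another cause among disease, drugs or chemicals (cannot explain it, unlikely, or plausible), and by whether it is incontrovertibly not related. An unlikely cause is taken as one that could still explain the event.

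The *unrelated* wording can be read in two ways:

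- Reading A: incompatible timing AND (could be explained OR incontrovertibly not related).
- Reading B: (incompatible timing AND could be explained) OR incontrovertibly not related.

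**Result for events not incontrovertibly unrelated.** The two readings agree:

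| Timing | Other cause | Labels met |
|---|---|---|
| Compatible | Cannot explain | *Possibly related*, *related* |
| Compatible | Unlikely | *Possibly related* |
| Compatible | Plausible | None |
| Incompatible | Cannot explain | None |
| Incompatible | Unlikely | *Unrelated* |
| Incompatible | Plausible | *Unrelated* |

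The third row is the gap at issue. The fourth row is a second gap of less consequence, since incompatible timing argues against an ADR. For a compatible-timing event with a plausible other cause, *unrelated* becomes available only if the event is incontrovertibly not related, and then only under reading B.

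**An illustration.** Suppose ALT rises after dosing in a subject taking paracetamol.

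1. *Related* fails, because another drug could explain the rise.
2. *Possibly related* fails, because attribution to that drug is not unlikely.
3. *Unrelated* fails on either reading, because timing is compatible and non-relation is not beyond dispute.

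So 0 of 3 labels fit. Protocol 6.4.1 names transaminase elevation as an expected ADR and Protocol 11.4 allows up to 4 g of paracetamol a day, so each half is foreseen, though no section links them. Protocol 14.5.10 requires a clinically significant laboratory abnormality to be reported as an AE, and 14.3 requires an opinion on relationship for every AE.

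**With the wording proposed under the fix.** If the drug is a reasonable possibility, the third-row event is *possibly related* (1 of 3). If not, it is *unrelated*. The fourth-row event is *unrelated*. Every row then has a label.

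**Limit of the gap.** The competing cause must be a disease, drug or chemical. An event whose only rival explanation is, say, a study procedure still meets *possibly related* literally.

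**The case against.** The strongest reply is that the plan already holds the right test. Protocol 14.1 ties *possibly related* to a reasonable possibility, SAP 11.3 repeats it, 8.5 leaves relatedness to the Investigator, and 14.2 treats alternative cause as one consideration among four. In the ALT illustration, earlier similar reactions would point towards the drug. This stands in part: an Investigator can reach the right label. Doing so means overriding the category text, because the four considerations assign no label.

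The second reply is that gap events should be uncommon. Protocol 9.3 excludes clinically significant disease history and most medication in the 14 days before dosing, and 11.4 keeps the medication limits until the follow-up call. What remains is mainly intercurrent illness, paracetamol, hormonal contraception, HRT and treatment for AEs. This stands.

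The third reply is that other protections do not need the label. These include individual withdrawal (8.3), SAC data review (8.2), urgent safety measures (16.2), SAE notification to the sponsor within 24 hours (16.3.1), the sponsor's own SUSAR classification (16.3.2) and TEAE tables regardless of causality (SAP 11.3.1.2). This stands too, and it limits the consequence. SAP 11.3 also tabulates an absent relationship as missing, but that handles absent data and does not give the Investigator a fourth label.

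**Conclusion.** The inconsistency is real and minor. It rests on a literal reading of 14.2, on a competing disease, drug or chemical cause that is not unlikely, and on an Investigator who applies the category text without going back to 14.1. Under those conditions an event that 14.1 would call an ADR can stay out of the 8.5 triggers, the 8.4 rule and the ADR tables. No objective based on PK is affected.

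Three stronger readings are tempting, and the documents do not support them.

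- *The halt rule will miss events.* The Investigator decides relatedness and may use 14.1, so a missed halt is possible but does not follow from the text.
- *The number of relabelled events can be bounded from the earlier oral Phase 1 rates in Protocol 5.3.2.* Those studies used a possible, probable or definite scale and single and multiple doses of 50 to 1600 mg. The rates cover only terms seen in at least 2% of subjects. Nothing shows that events judged not related there had compatible timing and a plausible other cause. Neither the frequency of gap events nor the effect on halting can be computed.
- *Section 8.5 also needs a severity rule for symptom-free ALT or QTcF threshold events.* Protocol 8.3 already lists those thresholds under serious or severe AEs, which can be read as prevailing over the functional scale in 14.1. Protocol 14.4.1 also lets the Investigator treat such an event as serious. Making it mandatory would change the stopping rule and is not part of this point.

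**What to change.** Amend two definitions in Protocol 14.2:

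- *Possibly related*: Clinical event with a reasonable time relationship to IMP administration, where the IMP is a reasonable possibility even if another cause is also plausible.
- *Unrelated*: every event meeting neither *possibly related* nor *related*.

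The first brings 14.2 into line with 14.1. The second gives every remaining event a label and closes the lesser gap as well. Sections 8.4 and 8.5 can stay as written, and SAP 11.3 needs no change because it already carries the 14.1 test.

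The cost is a short protocol amendment with no new procedure. The downside is a few more events labelled ADR and a slightly more sensitive halt. That matters because resuming after a halt needs a further substantial amendment approved by the MHRA and the ethics committee.
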